6.2. Study Procedures and Description of Assessments

A trained research staff member will explain the study to potential participants in a private location and give them a copy of the informed consent document to read. The staff member will review the risks and benefits of the study and ensure the potential subject understands the research. Once consent is given, the screening assessments will then be scheduled. Timing of assessments will be determined by participants' availability. Group assignment, main outcomes, and participant characterization measures are described below. **Table 1** lists assessments.

259 Group Assignment

Participants will be assigned to one of four groups, based on results of audiometric assessments and the Clinician 260 Administered PTSD Scale for DSM-5 (CAPS-5), explained below. Those who indicate they have bothersome tinnitus and 261 262 meet criteria for PTSD on the CAPS-5 (conducted by an independent evaluator), will be assigned the Tinnitus and PTSD Group (T&P). Those who do not endorse tinnitus and meet criteria for PTSD will be assigned to the PTSD Only Group 263 264 (PO). Those who indicate they have bothersome tinnitus but do not meet criteria for PTSD will be assigned to the Tinnitus Only Group (TO). Those who do not endorse tinnitus and do not meet PTSD criteria on the CAPS-5 will be assigned to 265 266 the Healthy Control Group (HC). All will then be scheduled for an fMRI scan. Participants will be matched across groups for sex, age, head injury, length of military service, number of deployments, and hearing loss. Measures used for group 267 268 assignment and characterization are explained below.

270 Assessment Instruments.

The audiometric assessments will be conducted at the Hearing Center of Excellence (60 minutes). Repeat tinnitus acoustic assessment only (see description below) may be completed at the RII prior to the fMRI for eligible participants with tinnitus when an evaluator is available (30 minutes).

Self-report instruments may be administered at the Hearing Center of Excellence, at the STRONG STAR offices, or via
 online data capture, Clinical interviews may be administered at the STRONG STAR offices or via phone or video
 conferencing. These assessments are estimated to take approximately 90 minutes.

278

282

284

269

274

258

fMRI scans will be conducted at the Research Imaging Institute (60-75 minutes). Participants will be asked whether they

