305	apply). Each nominal point will be scored separately, as either 0 (=not endorsed by participant) or 1 (=endorsed by
306	participant).
307	5. The Clinician-Administered PTSD Scale for DSM-5 (CAPS-5; Weathers, et al., 2013) is a semi-structured interview,
308	conducted by an independent evaluator, that measures DSM-5 symptoms of PTSD. Presence of at least one intrusion
309	symptom, one avoidance symptom, two cognition and mood symptoms, and two arousal symptoms for 1 month or more
310	are required to reach the diagnostic threshold. Selection of Index Event for CAPS-5 will be used as a supplement to the
311	CAPS-5 interview to help determine which event to select as the Index Event. This form is standardly used in conjunction
312	with the CAPS-5 and does not represent a separate assessment. The CAPS-5 will be used to determine whether
313	participants meet criteria for PTSD for group determination and is a central variable in the study.
314	6. PTSD Check List – DSM-5 (PCL-5). The PCL-5 (Weathers, et al., 2010) is a 20-item self-report measure update of the
315	PCL designed to assess PSTSD symptoms as defined by the DSM-5. The PCL-5 is currently available and has been
316	shown to have good psychometric properties. The PCL-5 evaluates how much participants have been bothered by PTSD
317	symptoms in the past month (for baseline and follow up assessments) as a result of a specific life event. Each item of the
318	PCL-5 is scored on a five point scale ranging from 0 ("not at all") to 4 ("extremely).
319	7. The Tinnitus Functional Index (TFI; Meikle et al., 2011) has documented validity for scaling the severity and negative
320	impairment of tinnitus for use in intake assessment, and for responsiveness to treatment. The TFI will be used to
320	
	determine group assignment and to control for tinnitus-related distress in analyses.
322	8. Resting-State Functional Magnetic Resonance Imaging (rs-fMRI). We will acquire BOLD fMRI images in an
323	unstimulated state using an extended time-series (300 whole-brain volumes over ~ 60-75 min). These data are a main
324	outcome. Data will be processed on an ongoing basis to ensure integrity, and includes controlling for white matter,
325	cerebral spinal fluid, and movement.
326	9. Hyperacusis Questionnaire (HAQ). The Hyperacusis Questionnaire (HAQ; Khalfa et al., 2002) is a self-report
327	questionnaire that evaluates various hyperacusis symptoms. The HAQ consists of three factors, including attentional,

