Participants who are eligible to continue in the study after consent and screening will undergo a resting-state function
magnetic resonance imaging (rs- fMRI) session at the Research Imaging Institute (RII) at the University of Texas Health
Science Center at San Antonio. Participants who cannot tolerate the MRI procedure will be withdrawn from the study. Each
MRI scan may take up to 75 minutes. Participants will be asked whether they hear their tinnitus before the MRI scan, whether

they heard the tinnitus during the scan, and whether their tinnitus changed since the last time asked. Data will be recorded on the Tinnitus Data Collection Page.

480

492

504

481 **6.3.2.3 Data Storage and Access:**

Data will be coded using an assigned number. Paper research data will be kept in locked file cabinets in locked offices at the University of Texas Health Science Center San Antonio (UTHSCSA) STRONG STAR offices; the Research Imaging Institute (RII), or the Hearing Center of Excellence at Wilford Hall Ambulatory Service Center at Lackland Air Force Base (HCE). Data collected will be entered into a spreadsheet located on a secure STRONG STAR server. Audio-recordings of assessments will be uploaded to a secure STRONG STAR server over an encrypted network connection.

Neuroimaging data will be kept on secure networks at the Research Imaging Institute. Audiometric data will be kept under
 lock and key at the HCE. Every member of the Research Team will be trained and monitored about how to handle and
 protect both medical and research records. Furthermore, the Research Team strictly controls access to study data using
 policies and procedures developed specifically for the STRONG STAR Research Consortium.

493 6.4 Statistical Consideration494

495 **6.4.1 Primary (i.e., primary outcome variables) and secondary endpoints.**

496
 497 Primary outcomes include results based on measures of PTSD (CAPS-5 and PCL-5) and tinnitus-related distress (TFI and
 498 TAQ). The additional primary outcome is changes in functional activity within resting-state networks, provided by fMRI scans.
 499

500 Secondary outcome variables include measures of depression and suicide (PHQ-9), anxiety (GAD-7), and alcohol use 501 (AUDIT). 502

503 **6.4.2 Hypotheses, Sample Size Estimation, and Specific Data Analysis Plans.**

505 Hypothesis 1: Canonical correlations will identify both shared and unique symptoms between tinnitus-related distress and 506 PTSD.

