507 Analysis Plan: Non-inferential statistics will be calculated to include central tendencies, standard deviations, and alpha coefficients. Prior to analyzing data, unusual distributions, missing data, or outliers will be identified. Descriptive 508 509 statistics will be used to summarize participant characteristics. Group differences will be tested using t-tests, Chi-Square, or Fisher's exact tests as needed. Canonical correlations will be conducted on the data of all 60 participants from the T&P 510 and TO groups, using the subscale scores of the CAPS-5 and the TFI. Canonical correlations identify and measure 511 512 associations among two sets of variables and will identify latent variables between tinnitus-related distress and PTSD 513 symptoms. The 12 total subscales from the CAPS-5 and TFI will be entered into the analyses, requiring 60 participants for 514 large effect sizes (Steven, 1986).

515

516 Hypothesis 2a: Dysregulated connectivity within the auditory-vigilance resting state network will be implicated among

517 individuals with both tinnitus and PTSD.

- 518 Hypothesis 2b: Individuals with tinnitus and PTSD will demonstrate unique patterns of dysregulation within the auditory-
- 519 vigilance network, versus those with only PTSD, only tinnitus, and healthy controls.

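### Aim 1 sorts symptoms into shared and unique by a canonical correlation of 12 subscales in 60 people, with no stated overfitting correction and no uncertainty on the loadings

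*Combined protocol and SAP*

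**What the plan says.** Hypothesis 1 reads: "Canonical correlations will identify both shared and unique symptoms between tinnitus-related distress and" PTSD. The analysis plan beneath it in section 6.4.2 is short. "Canonical correlations will be conducted on the data of all 60 participants from the T&P" and TO groups, on the subscale scores of the CAPS-5 and the TFI. The method is said to measure "associations among two sets of variables and will identify latent variables between tinnitus-related distress and PTSD" symptoms. On size, "The 12 total subscales from the CAPS-5 and TFI will be entered into the analyses, requiring 60 participants for" large effects, with a multivariate statistics textbook as the source.

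The other Aim 1 items are descriptive statistics, reliability coefficients, screening for outliers and missing data, and group comparisons ("Group differences will be tested using t-tests, Chi-Square, or Fisher's exact tests as needed"). The plan does not state:

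- how the 12 subscales divide between the two instruments;
- a test of the canonical roots, or an alpha for Hypothesis 1;
- a correction for overfitting;
- an interval or stability check for the loadings;
- a rule for calling a symptom shared or unique.

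**The concern.** Canonical correlation picks the weights on both sets that make the sample correlation as large as possible. With 12 variables and 60 people, much of that maximum can be chance. Two consequences need to be kept apart.

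The first is the coefficient itself. A sample value of 0.5 to 0.6 looks substantial but is ordinary when nothing is there.

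The second bears directly on the hypothesis. The only part of the output that speaks to single symptoms is the set of loadings (the correlation of each subscale with its canonical variate). If these move widely between samples of 60, a symptom called shared here might be called unique in the next study, and a reader given only point values could not tell.

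**Working it through.** **The plan's own figure.** Sixty cannot be derived from the plan's inputs, because Hypothesis 1 has no alpha, power or numerical effect. The only arithmetic that matches is five people per variable, 5 x 12 = 60, and the plan does not state that rule.

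**Inputs.**
- n = 60 and 12 subscales: section 6.4.2.
- Split 4 + 8: assumed. The CAPS-5 entry in section 6.2 counts symptoms in four clusters (one intrusion "symptom, one avoidance symptom, two cognition and mood symptoms, and two arousal symptoms for 1 month or more"), and 12 - 4 = 8.
- Alpha 0.05, normal data and within-set correlation r = 0.3: assumed. Other values are shown where they matter.

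**Formulas.** The first canonical correlation is the maximum of corr(Xa, Yb) over weights a and b. Wilks' lambda is the product of (1 - r_i^2) over the roots, tested by Rao's F. The loading of subscale j is corr(Y_j, Yb).

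**Step 1: no association.** One fixed CAPS-5 score regressed on eight unrelated TFI scores has expected R^2 = 8/59 = 0.136, or R of about 0.37. Choosing the best of all weightings of four CAPS-5 scores pushes this higher. By simulation the first canonical correlation averages 0.51 (5th to 95th percentile 0.41 to 0.62) and reaches 0.5 in about 58% of datasets. Splits of 3+9, 5+7 and 6+6 give means of 0.50, 0.52 and 0.52. Only very lopsided splits fall lower (0.47 at 2+10, 0.42 at 1+11). The Wilks test keeps its size (about 5%).

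**Step 2: a real association.** One non-zero root runs through two CAPS-5 and three TFI subscales with equal weights. True TFI loadings at r = 0.3:
- linked: (1 + 2r)/sqrt(3 + 6r) = 1.6/2.19 = 0.73
- unlinked: 3r/sqrt(3 + 6r) = 0.9/2.19 = 0.41

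| True value | Mean sample value | Mean 5-fold cross-validated value | At least two of three linked subscales in top three | All three |
|---|---|---|---|---|
| 0 | 0.51 | 0.00 | - | - |
| 0.5 | 0.63 | 0.27-0.30 | 82% | 27% |
| 0.6 | 0.69 | 0.42-0.43 | 92% | 41% |
| 0.7 | 0.76 | 0.57 | 97% | 59% |

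5th to 95th percentile of the estimated loadings:
- true 0.5: linked 0.18 to 0.84, unlinked -0.09 to 0.67
- true 0.6: linked 0.37 to 0.85, unlinked 0.03 to 0.64

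**Step 3: does a significant test cure it?** Hardly. Among datasets with Wilks p < 0.05, the share with all three linked subscales on top moves from 27% to 28% at a true 0.5, and from 41% to 44% at 0.6.

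**Step 4: dependence on the model.** With r between 0 and 0.6 and a true 0.5, all three are on top in about 13% to 50% of datasets, and at least two in 66% to 93%. In a different structure (half of each set with true loading zero, absolute loading of 0.3 or more read as shared), about 3 of 12 subscales are misclassified at a true 0.5, about 2 at 0.6 and about 1 at 0.7.

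**The case against.** **Silence is not a plan to skip the test.** A reader might infer that the sponsor will report an untested coefficient as evidence. Section 6.4.2 does not say so. Most analysts would run Wilks' test as a matter of course, and it removes the risk of calling noise an association. This stands: the unnamed test is missing detail only.

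**The plan is sized for large effects.** If large means 0.7, the loadings are much steadier and at least two of three linked subscales surface in 97% of datasets. This stands in part. The plan gives no number, so 0.5 cannot be excluded, and at 0.5 the ranges overlap heavily.

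**Exact ranking is a harsh yardstick.** Hypothesis 1 does not ask for a top three, and the 27% depends on a within-set correlation that the documents do not give. This stands; the overlap of the loading ranges is the fairer measure.

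**Sixty is too few.** This is a tempting inference, but the documents give nothing against which the figure can be tested, so it cannot be called wrong.

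**Pooling manufactures the association.** The groups are split on the CAPS-5 diagnosis: "Those who indicate they have bothersome tinnitus but do not meet criteria for PTSD will be assigned to the Tinnitus" Only group. A TFI difference between them would therefore enter the pooled result. But both groups are selected for bothersome tinnitus, no TFI difference is documented, and the planned group tests could show one. Partialling out a group that is itself a cut of the CAPS-5 would also discard true signal. With a dimensional link of 0.61, for example, power falls from 82% pooled to 33% adjusted. The documents do not support making this a finding.

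**Conclusion.** The point holds in a limited form: a cheap improvement, not a flaw that makes the data unusable. Hypothesis 1 rests on loadings for which the plan states no uncertainty, and on a coefficient for which it states no correction. The inflation of the coefficient (0.51 on average under no association, 0.63 at a true 0.5) is well established for any split from 3+9 to 6+6. It means that size should not be read as strength. Loading instability is what remains after a significant root test. It is marked at a true 0.5 and milder at 0.7, and its exact size depends on an assumed structure, within-set correlation and normality. A reader should not conclude that most shared or unique calls would be wrong. The supportable conclusion is that point loadings alone cannot show which calls are secure.

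**What to change.** In the Hypothesis 1 analysis plan (section 6.4.2):

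1. State the subscale split, and test the roots in sequence by Wilks' lambda or permutation at a stated alpha.
2. Beside the sample canonical correlation, report a repeated cross-validated value. Say that it is conservative (about 0.3 at a true 0.5) and noisy (5th to 95th percentile -0.01 to 0.58 there).
3. Report sign-aligned, bias-corrected bootstrap intervals for every loading and call them approximate. For linked subscales at a true 0.5, nominal 95% intervals cover about 84% at within-set r 0.3 and 74% at 0.6. Plain percentile intervals do worse (78% and 53%).
4. Report all pairwise CAPS-5 by TFI subscale correlations (4 x 8 = 32 under the assumed split) with 95% intervals. These hold their coverage (0.950 to 0.953 in simulation).
5. Call a symptom shared or unique only where its interval supports that, against a loading value written down beforehand. Otherwise call it undetermined.

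The cost is analysis code and a paragraph of SAP text, with no new data or participants. The real downside is fewer firm shared or unique calls.

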Overlapping Symptoms and Comorbidity. The same traumatic event could cause PTSD and tinnitus (e.g., IEDs). Tinnitus 61 62 can be conceptualized as a conditioned stimulus, reminding the individual of the traumatic event (Criterion B of PTSD; APA, 2013), as in flashbacks (Hinton et al., 2006). Those with tinnitus also show symptoms of avoidance (Criterion C of 63 PTSD). Veterans with both tinnitus and PTSD, and those with only tinnitus, reported similar aversions to loud signals and 64 65 lower tolerance to loud noises (Fagelson, 2007), which may result in decreased social interaction and engagement in pleasurable activities (Jastreboff & Jastreboff, 2002). Negative alterations in mood and cognition (Criterion D of PTSD) are 66 67 observed in those with tinnitus, and tinnitus-associated trauma and catastrophic cognitions predict PTSD severity (Hinton et al., 2006). Finally, individuals with tinnitus show emotional reactions that overlap with vigilance or hyperarousal 68 69 (Criterion E of PTSD), including startle responses, anger, and irritability (Fagelson & Smith, 2016), and sleep disturbance (McKenna, 2000). The high comorbidity between tinnitus and PTSD also suggests a common etiology that leads to 70 impairment and distress. Our recent study ([name] et al., 2020a) found a latent factor between tinnitus-related distress 71 72 and PTSD symptoms among veterans with PTSD, tinnitus, and posttraumatic headache. Based on this evidence, we posit 73 that PTSD exacerbates impairment among individuals with tinnitus. More research is needed to investigate psychiatric contributions to tinnitus-related distress, such as PTSD, with a possible unique phenotype when tinnitus and PTSD co-74 occur.

75 oc 76

Functional Outcomes. Functional outcomes for those with both tinnitus and PTSD are significantly worse than those with
 tinnitus only, or tinnitus and any other psychological disorder (Fagelson & Smith, 2016). This suggests a particularly
 deleterious combination of symptoms that exacerbate, and possibly maintain each disorder. It is feasible to treat
 psychiatric distress, and if successful, tinnitus-related distress will also decrease. Civilians with tinnitus had less tinnitus related distress after receiving trauma-focused therapy (Rikkert et al., 2018), but they were not evaluated for PTSD.
 These studies demonstrate the association between tinnitus and PTSD. More research is warranted to elucidate the

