Analysis plan: rs-fMRI provides valuable information about neurobiological mechanisms that influence 520 neurological and psychiatric conditions at rest (Menon, 2011). To test our conceptual model and deduce neurobiological 521 mechanisms, we will use an existing, well-documented, 20-component parcellation scheme of the resting-state networks 522 (Laird et al., 2011; Auditory Component 16). After extracting the A1/VAN, we will use group information-guided 523 524 independent components analysis (GIG-ICA) to determine intra-network connectivity differences between those with both 525 tinnitus and PTSD, only PTSD, only tinnitus, and healthy controls. Our team (Vanasse et al., 2019) found robust 526 differences between active-duty service members with PTSD, combat controls, and civilian control (50 active-duty with 527 PTSD, 28 combat-exposed controls, and 25 civilian controls). Based on those results, 120 participants (30 per group) in 528 this proposed study, a priori power analyses demonstrated power of 80% when $\alpha = 0.05$, to detect an effect size of d = 529 0.31 (ANOVA: Fixed effects, omnibus one-way; Faul et al., 2007). Secondary analyses will examine functional connectivity between A1/VAN and other resting-state networks. 530 531

532 Hypothesis 3: Dysregulated activity within regions of the auditory-vigilance network will be correlated with symptom 533 clusters of both tinnitus-related distress and PTSD.

534 Analysis plan: Correlations will be conducted between functional connectivity within the auditory-vigilance resting state 535 network with tinnitus-related distress and PTSD symptoms. Power analyses predict that 57 participants will achieve a 536 power of .95, with an effect size d = .45, and alpha = .05 (R Core Team, 2014).

538 Missing data. If missing data can be assumed to be missing at random, likelihood-based mixed model analysis will 539 provide valid inferences using data from all cases with any outcome data. The impact of attrition on analyses will be addressed by comparing those who are available for analysis at each assessment with those who are not using 541 appropriate data from prior assessments. 542

543 6.5 Confidentiality

537

544

554

557

563

564

568

569

570

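### If PTSD is more severe in T&P than in PO, a Hypothesis 2b difference could reflect severity rather than a distinct comorbid phenotype, because severity is neither matched nor adjusted for

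*Combined protocol and SAP*

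**What the plan says.** Hypothesis 2b (sections 3 and 6.4.2) predicts that "Individuals with tinnitus and PTSD will demonstrate unique patterns of dysregulation within the" auditory-vigilance network, against PO, TO and HC. The analysis plan in section 6.4.2 uses GIG-ICA "to determine intra-network connectivity differences between those with both" conditions and the other three groups. It names no covariates.

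Section 6.2, Group Assignment, matches on sex, age, head injury, "length of military service, number of deployments, and hearing loss". The CAPS-5 assigns groups by whether diagnostic criteria are met. Section 6.2 says that the TFI will be used to control for tinnitus-related distress, and audiometry to control for tinnitus pitch and loudness and for hearing loss. It says nothing comparable about CAPS-5 or PCL-5 severity. Table 1 links both measures to Aim 2 without stating an adjustment use.

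Hypothesis 3 expects activity in the same network to correlate with PTSD symptom clusters. Sections 2, 4 and 7.2 connect the comorbidity to a different phenotype that may explain poor response to PTSD treatment.

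**The concern.** Confounding of T&P versus PO by severity needs two links, and the protocol gives grounds for both.

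- **Severity to connectivity.** This is Hypothesis 3. Section 4 also ties the A1/VAN to the arousal symptoms of PTSD.
- **Comorbidity to severity.** The Functional Outcomes paragraph of section 4 suggests that the combination may worsen and sustain both disorders. The preceding paragraph says that trauma and catastrophic thinking related to tinnitus predict how severe PTSD is. It also lists startle, irritability and poor sleep among people with tinnitus, and these overlap with CAPS-5 items.

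Both groups must pass the same diagnostic threshold, but a threshold sets only a minimum, so mean severity above it can still differ. If it does, part or all of a T&P versus PO difference could be the same disorder in a more severe form. That reading and a distinct phenotype have different implications for the treatment argument.

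**Working it through.** **Inputs.** From section 6.4.2: "Based on those results, 120 participants (30 per group"), alpha 0.05, 80% power, effect size 0.31 for a one-way omnibus ANOVA; and for Hypothesis 3, effect size 0.45, 57 participants, power .95. Assumed, because the documents give no values: the T&P minus PO gap in CAPS-5, D, in within-group SD units; and the within-group correlation r between CAPS-5 and connectivity.

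**Step 1: the plan's own figures.**
- Omnibus ANOVA, 4 groups, N = 120, noncentrality 0.31² × 120 = 11.53. Power is 0.810, against the stated 80%. It reproduces with 0.31 read as Cohen's f, although the plan labels it d.
- Hypothesis 3, Fisher z with r = 0.45 and N = 57: atanh(0.45) × √54 = 3.56, and 3.56 − 1.96 = 1.60, so power is 0.945, against the stated .95. The 0.45 therefore works as a correlation, although it too is labelled d.
- The omnibus power does not carry over to one pair of groups. With 30 versus 30, 80% power requires d of about 0.74.

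**Step 2: difference induced by severity alone.** With no tinnitus-specific effect, the induced d is r × D. The rejection rate comes from the two-sided noncentral t with 58 degrees of freedom and noncentrality r × D × √(30/2).

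| D (SD) | d at r = 0.45 | rejects | d at r = 0.30 | rejects |
|---|---|---|---|---|
| 0 | 0 | 5.0% | 0 | 5.0% |
| 0.25 | 0.11 | 7.1% | 0.08 | 5.9% |
| 0.5 | 0.23 | 13.7% | 0.15 | 8.8% |
| 0.8 | 0.36 | 27.8% | 0.24 | 15.0% |
| 1.0 | 0.45 | 40.3% | 0.30 | 20.8% |

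**Step 3: which r is plausible.** The plan does not say who the 57 participants are. If they mix people with and without PTSD, 0.45 is a pooled correlation and the within-PTSD value is lower. Assume two equal halves that differ by 2 to 3 within-group SD on CAPS-5. The pooled variance of CAPS-5 is then 1 + D²/4, that is 2 to 3.25. Dividing 0.45²/(1 − 0.45²) = 0.254 by these gives 0.127 to 0.078, so the within-group r is about 0.34 to 0.27. The r = 0.30 columns represent this case.

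**Step 4: adjustment when severity is a confounder.** Simulation with 20,000 runs, r of 0.2 to 0.45 and D of 0, 0.5 and 1 SD. With CAPS-5 as covariate, the false-positive rate is 4.7% to 5.1% throughout. Power for a true d of 0.74 is 0.79 to 0.88 for D of 0 or 0.5, and 0.72 to 0.80 for D of 1.

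**Step 5: adjustment when severity is a consequence of connectivity.** Let group change connectivity by d = 0.74 and connectivity drive CAPS-5. The adjusted difference is then 0.74 × (1 − r²). At r = 0.45 this is 0.74 × 0.7975 = 0.59, and power falls from 80% to 69%, or to 67% if both tests had to be significant. At r = 0.30 the corresponding figures are 0.67, 75% and 73%.

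**The case against.** The strongest reply concerns the premise. A reader might infer that T&P will have more severe PTSD than PO, and so that a false phenotype claim is to be expected. The documents do not support that. They give no CAPS-5 mean for either group. The sentence most likely to be cited, "Functional outcomes for those with both tinnitus and PTSD are significantly worse than those with", goes on to name tinnitus alone, or tinnitus with another psychological disorder, as the comparators; PO is not among them. Section 4 also proposes that PTSD worsens impairment in people with tinnitus, which is the other direction. This part of the reply stands, so the point is conditional.

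Second, adjustment may remove real signal. Section 4 treats A1/VAN dysregulation as a cause of symptoms, which would put CAPS-5 downstream of the outcome. Step 5 shows the cost. This also stands, and it rules out the tempting stricter rule of calling a pattern unique only if both tests are significant.

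Third, severity alone predicts more of the same regional pattern, and one two-group test is not the false-positive rate for a regionally distinct one. That is fair: the rates above apply to one connectivity measure. But the plan gives no definition of unique that separates a different pattern from a stronger one.

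Fourth, section 6.4.2 plans descriptive group tests, and Hypothesis 3 examines severity. These could show an imbalance, but no step in the Hypothesis 2b analysis follows from it.

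**Conclusion.** The omission is confirmed: PTSD severity is neither a matching variable nor a stated covariate for Hypothesis 2b, although tinnitus distress and audiometric measures are named as controls. The consequence depends on two quantities that the documents do not give. With no severity gap there is no inflation. At 0.25 SD the false-positive rate is 6% to 7%, at 0.5 SD 9% to 14%, and at 1 SD 21% to 40%, for r of 0.30 to 0.45. This does not show that a T&P finding would be false. It shows that the planned contrast could not by itself attribute a difference to comorbidity rather than severity if the groups prove unequal. The conclusion does not turn on the sample size.

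**What to change.** In section 6.4.2, under Hypotheses 2a and 2b:

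- Pre-specify the T&P versus PO contrast twice, unadjusted and with CAPS-5 total as a covariate, fitted within these two groups.
- Report the T&P minus PO difference in CAPS-5, with its interval, beside both results.
- Treat the adjusted result as a sensitivity analysis. Describe a pattern as independent of PTSD severity only if it persists after adjustment; otherwise state that it cannot be separated from severity. Do not require both tests to be significant.

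The cost is one extra model on the 60 T&P and PO participants, with data already to be collected. It uses one degree of freedom and widens the interval if severity differs. It may over-adjust if severity is a result of the connectivity change, which is why both results should be shown. Fixing it before results are seen avoids a post hoc choice on the study's central claim.
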